## **5.6 Measures of Adaptations, Feasibility, Usability, and Acceptability of OST-S**

Adaptations to OST-S made by school partners in providing additional support to students at the group or student level will be assessed by the following measures.

**Survey of OST Adaptations and Supplementary Supports for Individual Students** – This measure was developed by the investigative team. This measure will be collected from school partners (per student) at post-treatment, 5-month follow-up, and 12-month follow-up. The measure is designed to capture when school partners contribute extra supports above and beyond what is outlined in the treatment manual for them to provide to students in the Organizational Skills Training School-based program (OST-S).

---

**Survey of OST Adaptations and Supplementary Supports for Groups** – This measure was developed by the investigative team. This measure will be collected from school partners at post-treatment (per group). The measure is designed to capture when school partners prepare/provide additional supports for students beyond that outlined in the treatment manual as they implement the Organizational Skills Training School-based program (OST-S).

Feasibility and usability will be assessed by monitoring of intervention fidelity, participant engagement, and adherence.

**The Treatment Evaluation Inventory – Short Form (TEI-SF)**, a 9-item measure, will be used to assess parents' views of treatment acceptability (Kelley et al., 1989).

**The Children's Intervention Rating Profile (CIRP)**, a 7-item measure, will be adapted to assess student's perceptions of acceptability (Witt & Elliott, 1985).

**The Usage Rating Profile–Intervention–Revised (URP-IR)**, a 29-item measure, will be adapted (with permission) to assess multiple factors that may influence the usage of the OST-S intervention in a school-based setting – for example: acceptability, understanding, home school collaboration, feasibility, system climate, and system support (Chafouleas, Briesch, Neugebauer, & Riley-Tillman, 2011).

## **5.7 Cost Analysis Measures**

Main cost item for the OST-S is the time spent by school partners, trainers/consultants, and experts from the investigative team on intervention activities which may be collected using time diaries. Costs for the OST-S group may include: (a) initial training time of the study team trainers; (b) initial training time of the school partners; (c) subsequent supervision time of study team trainers; (d) subsequent consultation and coaching time provided to the school partners; (e) school partner implementation of OST-S groups with eligible students (including consultation with parents and teachers to promote generalization); and (f) consultant (post-doctoral fellow) time necessary to maintain relationships with participating schools and support ongoing implementation of the OST-S program. For each component, two main types of costs will be calculated: (1) cost of physical materials used for training and interventions and (2) costs associated with time spent for training, supervision, and intervention implementation (Blonigen et al., 2008).

Intervention and training/consultation times will be derived from administrative records of OST-S session times and student attendance, and diaries completed by interventionists, trainers/consultants, and experts, during four, 1-week periods throughout the trial.

## **6 STATISTICAL CONSIDERATIONS**

### **6.1 Main Study Analysis**

#### **6.1.1 Study Aims**

**Aims 1 and 2: Effect of Intervention on Proximal and Distal Outcomes.** Linear mixed effects models with random intercepts and slopes for school (the cluster), and fixed effects for intervention, time, and time-by-intervention interaction (the estimate of interest) will be applied. Random effects account for inter-school variation in the effect of the intervention over time.

**Aim 3: Mediation Effects.** This aim explores the effect of potential mediating variables (M; OTMP skills, self-efficacy) on the effect of the intervention (A) on student academic outcome (Y). Our goal is to understand the mechanism of change in student performance due to the planned intervention. In this context, we will examine two levels of mediation: school-level average organization skills associated with school-level academic performance, and student-level organization skills and performance.

**Aim 4: Association Between Fidelity/Engagement and Outcomes:** To determine whether fidelity and engagement are associated with outcomes, we will describe the impact of these factors on outcomes, with special attention to variation in outcomes across schools. These associations will not benefit from randomization (fidelity and engagement are post randomization interim process endpoints). For that reason, our assessments will be largely descriptive and qualitative, and will include assessment during the follow-up periods.

**Aim 5: Effect Modification:** Aim 5 explores potential moderating variables (i.e., gender, grade level, family SES, special education status, and severity of ADHD, externalizing and internalizing behaviors). Because these potential effect modifiers vary within the unit of randomization (school), these contrasts are essential within-cluster comparisons with good statistical power (see below). Effect modification can be estimated using the mixed effects and longitudinal models outlined previously.

**Aim 6: Cost and Cost Effectiveness.** We will estimate the incremental costs and incremental cost effectiveness (ICE) of OST-S. An ICE ratio will be constructed for each outcome measure with effects that differ significantly from the control group. The ICE will be determined based on differences in direct costs and will be calculated based on differences in mean costs for each condition, divided by the mean difference in outcomes (e.g. ratings of organizational skills and academic performance).

In many OST-S schools, the same school partner will provide intervention during both years of participation. In addition, we expect that many teachers who receive consultation during the first time will be involved again the second time. It is possible that school partners and teachers will be more effective in implementing OST-S later in the study than earlier, which could have some effect on outcomes. Our team will perform sensitivity analyses to determine whether response to intervention in OST-S schools differs for students enrolled earlier versus later in the study.

We anticipate that some of the students in the study will be medicated for ADHD. Medication status did not moderate outcomes for students included in study of OST-C ([name], et al., 2014). During baseline, post-treatment, and follow-up assessments, we will obtain information about student medication status. In the analyses, we will explore whether medication status has an effect on outcomes.

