### 2.2 Secondary Objectives (or Aims)

The secondary objectives of this study are:

- Explore whether reductions in student OTMP skills deficits and improvements in student academic self-efficacy mediate the effect of OST-S on students' academic outcomes.
- Investigate whether school partner implementation fidelity and participant engagement (student, parent, teacher) are associated with the effect of OST-S on student OTMP skills deficits.
- Investigate whether student grade level, special education status, and symptoms of ADHD, externalizing, internalizing problems, and symptoms of autism spectrum disorder moderate the effect of OST-S on student OTMP skills.
- Determine the costs associated with providing the OST-S intervention per group per school relative to student proximal (OTMP skills, self-efficacy) and distal (academic productivity and grades) outcomes.
- Investigate child in-session engagement in the OST-S intervention and the clinical factors associated with child engagement

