[name] calculations were performed using PASS 11 (Hintze, 2011; [www.ncss.com](http://www.ncss.com)), which demonstrated 90% power to detect a change in outcomes equivalent to 0.5 or greater in cross-sectional SDs, assuming at least 12 students per school and model correlation of these scores within student over time (corr=0.7), and assuming an ICC of 0.038 (a relatively large degree of variation across schools). A change equivalent to 0.5 cross-sectional SDs in outcome scores and 12 students per school is still detectable (power>0.85) if the correlation within students over time is 0.7 and the ICC across schools is 0.038. Larger effects can be detected with greater power. These power estimates apply to both OTMP skills and academic outcomes using intervention as a binary outcome in an intent-to-treat analysis. Based on the pilot study of OST-S, we expected effect sizes for outcomes to be in the 0.6 to 0.8 range. These power calculations are likely conservative; inclusion of covariates might actually improve power.

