### 6.1.5 Secondary Objectives

**Mediation effects.** For this Aim, we rely on our own simulations as well as two programs in the R package. We assumed 220 evaluable students across 20 schools, and a design effect of 1.1. In brief, David Kenny's program "PowMedR" (Kenny 2016) suggests that power is adequate to detect an effect size of 0.3 SD for both the effect of treatment (A) on the mediator (M) and the effect of M given A on Y (conditional effect of OTMP on outcome). Likewise, the R package "medssp" (Vittinghoff 2015) suggests adequate power ( $> 0.8$ ) to detect effect sizes of 0.4 jointly and separately for both the association of A and M (effect of intervention on OTMP skills) and OTMP skills on academic performance (association of M and Y). Our own simulations, conducted using Stata v 14.1, to determine power to rule out a direct effect (of the intervention on outcomes not mediated by OTMP skills) suggest that only a large direct effect can be ruled out at conventional levels of statistical significance using the planned sample. 95% confidence intervals of results of all analyses will reflect post hoc power.

**Association between fidelity/engagement with OST-S, child clinical factors, and outcomes.** Descriptive and qualitative analyses will be used, so power calculations were not conducted.

**Moderation effects.** [name] to detect an interaction of treatment (A) and a modifier with 25% prevalence was estimated to be greater than 85% assuming a main effect of treatment of 0.5 SD and design effects from the clustering of students within school in the range noted previously noted, for an interaction effect of 0.67 SD. Owing to the absence of software for testing interaction effects, these estimates are based on our simulations conducted using Stata v 14.1. While these estimates continue to reflect the clustered (by school) design, the design effect in practice for the interaction of an across-cluster (intervention) and a within-cluster (student characteristic) variable tends to be much lower than for a main effect (intervention only). We choose a binary moderator for this calculation, and 25% prevalence, to be somewhat conservative. Prevalence of some moderators (e.g., inattention) are likely to approach 50%.

Descriptive methods will be used to examine costs and cost effectiveness. As such, power calculations were not conducted.

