Linear mixed effects models were used to estimate the effects of OST-T2 on outcomes. Models had three levels: assessment time nested within student and students nested within school. All models included time (as splines), treatment, and time-by-treatment interactions. Mixed effects models included random intercepts for school (to account for clustering of students within schools), random slopes (over time) to allow for different trajectories across schools, and a random intercept and random slope for student to allow for variation in the effect of treatment assignment across students over time. Modeling for the clustering effect of schools accounted for more than one student being rated by multiple teachers; teachers rated a mean of 1.6 students and approximately 85% of teachers rated three or fewer students at each time point. Statistical significance was evaluated using a threshold p value of .0083, accounting for the estimation of three contrasts of time-by-treatment differences per outcome and two measures per domain (OTMP skills [COSS-P, COSS-T], homework performance [HPC, HPQ-T], and academic performance [ACES, APS]).

Mixed effects models facilitated both the graphic display, and contrasts, of curves depicting the expected values of outcomes over time from time zero until 12-month follow-up for the student with the last data collected. All confidence bounds reflected variances based on the multi-level linear model. To evaluate differences between conditions, we estimated model-based, expected values for outcomes at four preplanned times, 0 (baseline), 14 (post-treatment), 22 (5-month follow-up) and 55 (12-month follow-up) weeks, except for academic grades, which

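### Cost-effectiveness ratios are planned only for outcomes that reach significance, so they are reported selectively and, for outcomes with modest true effects, rest mainly on overestimated benefits

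*Protocol*

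**What the plan says.** Protocol 6.1.1, Aim 6, plans incremental costs and incremental cost effectiveness of OST-S. It then limits the ratios: "An ICE ratio will be constructed for each outcome measure with effects that differ significantly from the control group". Each ratio is the difference in mean costs between conditions "divided by the mean difference in outcomes (e.g. ratings of organizational skills and academic performance".

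Two other places in the protocol bear on this rule:

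- Section 2.2 states the objective as costs "relative to student proximal (OTMP skills, self-efficacy) and distal (academic productivity and grades) outcomes", with no significance condition.
- Section 6.1.5 says "Descriptive methods will be used to examine costs and cost effectiveness" and gives no power calculation for that reason.

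Aim 6 gives no significance threshold, no assessment time for the gate, and no interval for the ratio. The SAP contains no cost analysis. Its only stated threshold belongs to the outcome models: "Statistical significance was evaluated using a threshold p value of .0083".

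**The concern.** There are two problems, and the first needs no arithmetic.

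**Selective reporting.** Sections 5.2 and 5.3 list nine outcome measures (COSS-P, COSS-T, PALS, APR, ACES, grades, homework survey, HPQ-T, HPC), each at three post-baseline times. That makes 9 × 3 = 27 possible ratios. Which of them appear depends on p-values at an unstated threshold and time. The missing ones are the outcomes where OST-S adds cost without a clear benefit, which a school weighing the programme also needs to see. A significance gate also fits poorly with an analysis described as descriptive.

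**Selection on the denominator.** The estimate that must pass the test is the one the cost is divided by. The gate discards low estimates and keeps high ones. Where power is low, the retained effect is too large on average and the cost per unit of benefit looks too small.

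**Working it through.** **Inputs.** From Protocol 6.1.4: 120 students per arm after 15% loss, 12 per school, ICC 0.038, and within-student correlations of 0.5 to 0.7. The planned effect is 0.5 SD and the expected range is 0.6 to 0.8 SD. From the SAP: threshold 0.0083, which is 0.05/6. My assumptions are a two-sided alpha of 0.05 for the power figure (none is stated), true effects of 0.3 and 0.4 SD for weaker outcomes, and either 0.05 or 0.0083 as the gate's threshold.

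**Standard error.** Design effect = 1 + (12 − 1) × 0.038 = 1.418. The SD of change is √(2(1 − r)), which is 0.775 at r = 0.7 and 1.0 at r = 0.5. SE = SD × √(2 × 1.418/120) = SD × 0.1537, which gives 0.119 and 0.154.

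**The plan's own power figure.** Section 6.1.4 "demonstrated 90% power to detect a change in outcomes equivalent to 0.5 or greater in cross-sectional SDs" at correlation 0.7 and ICC 0.038. It then says that the same effect "is still detectable (power>0.85) if the correlation within students over time is 0.7 and the ICC across schools is 0.038". With the SEs above, power at 0.5 SD is 98.7% at r = 0.7 (97.8% using t on 18 df) and 90.2% at r = 0.5 (86.8% using t on 18 df). The stated figures are recovered only at r = 0.5, so I carry both correlations.

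**Effect of the gate.** An estimate qualifies if it exceeds c = z × SE. At p<0.05 (z = 1.96), c is 0.233 to 0.301 SD. At p<0.0083 (z = 2.64), c is 0.314 to 0.406 SD. For a true effect θ, put k = (c − θ)/SE. The mean retained effect is θ + SE × φ(k)/(1 − Φ(k)).

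Example: θ = 0.3, r = 0.5, p<0.0083. Then k = (0.406 − 0.3)/0.1537 = 0.69 and φ(k)/(1 − Φ(k)) = 1.28. The mean retained effect is 0.3 + 0.1537 × 1.28 = 0.497 SD, which is 1.66 times the truth.

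The last column below is the mean of θ/estimate among qualifying estimates, with incremental cost held at its true value. Each range runs from r = 0.7 to r = 0.5.

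| True effect (SD) | Threshold | Qualifies | Mean retained effect / true | Mean ratio / true |
|---|---|---|---|---|
| 0.3 | 0.05 | 71–50% | 1.19–1.41 | 0.88–0.74 |
| 0.3 | 0.0083 | 45–25% | 1.35–1.66 | 0.76–0.62 |
| 0.4 | 0.05 | 92–74% | 1.05–1.17 | 1.01–0.90 |
| 0.4 | 0.0083 | 76–49% | 1.12–1.32 | 0.93–0.78 |
| 0.5 | 0.05 | 99–90% | 1.01–1.06 | 1.05–1.00 |
| 0.5 | 0.0083 | 94–73% | 1.03–1.14 | 1.01–0.91 |
| 0.6 | 0.05 | >99–97% | 1.00–1.02 | 1.04–1.05 |
| 0.6 | 0.0083 | 99–90% | 1.00–1.05 | 1.04–0.99 |
| 0.8 | either | >99% | 1.00 | 1.02–1.04 |

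Mean ratios slightly above 1 at high power come from dividing by a noisy estimate, not from the gate. At 0.6 SD and r = 0.7, the first-order term is 1 + (0.119/0.6)² = 1.04, and the median ratio there is 1.00 of true.

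**The case against.** A reader might infer that the rule makes OST-S look cheaper per unit of benefit across the board. The documents do not support that. The trial was planned on 0.5 SD with 0.6 to 0.8 SD expected. On those figures the mean gated ratio runs from 9% low in the worst case to 5% high. No main-effect assumption of 0.3 SD appears in the plan; that size occurs only in the mediation power paragraph of 6.1.5, as a detectable effect. Applying the SAP's 0.0083 to the cost gate is also an assumption.

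A reader might also infer that outcomes missing significance lose all cost-effectiveness information. They lose only the ratio. Incremental cost is planned without a gate in Aim 6, and effects are estimated for every outcome under Aims 1 and 2 and in the SAP. Section 2.2 does not literally demand a ratio per outcome. The gate has a rationale too, because a ratio with a near-zero or wrong-signed denominator is unstable. On intervals, the mediation paragraph of 6.1.5 mentions 95% intervals for all analyses, so their absence here is arguable, though no method for a ratio is given.

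All of this stands, and it limits the size of the bias. It does not make modest effects implausible. The expected 0.6 to 0.8 SD comes from a pilot of 31 students analysed with within-group tests (Protocol 1.3), which are not differences from a control group. The controlled evidence in the same section, from the clinic version against waitlist, gives d = .42 for academic proficiency, close to the 0.4 SD rows. Nor does it answer the selective reporting, since instability can be handled without a p-value gate.

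**Conclusion.** The concern holds in limited form. The firm part is selective reporting: Aim 6 withholds ratios for outcomes without a significant benefit, at an unstated threshold and time point. This sits poorly with the all-outcome objective in 2.2 and the descriptive status in 6.1.5, and nothing else in the documents offsets it.

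The bias in the ratio is conditional. It is material for true effects of about 0.3 SD (mean ratio 0.62 to 0.88 of true across both thresholds) and smaller at 0.4 SD (0.78 to 1.01). At the planned 0.5 SD it is 0.91 to 1.05, and at 0.6 to 0.8 SD it is negligible (0.99 to 1.05). These figures rest on the sample size and ICC in 6.1.4, normal estimates, a fixed incremental cost and gating in the favourable direction. A general claim that OST-S is made to look too cheap would go beyond them. The point concerns one secondary aim and does not touch the primary efficacy comparison.

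**What to change.** Remove the significance condition from Aim 6. For every pre-specified proximal and distal outcome, at one named assessment time, report incremental cost, incremental effect and the ratio whatever the p-value. Take the interval from a bootstrap that resamples whole schools. Where the effect is near zero or its sign is uncertain, show cost and effect separately or on the cost-effectiveness plane instead of relying on the ratio. Put this in the SAP, which at present has no cost analysis.

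The cost is slightly more analysis and no new data. Some ratios will be unstable with wide intervals, and with only about ten schools per arm the bootstrap intervals will be approximate. The report should say both.

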### 6.1.2 Primary Endpoint

The primary endpoints are student OTMP skills and student academic self-efficacy, measured at post-treatment, 5 months from baseline and 12 months from baseline and compared between the intervention condition and the TAU condition.

---

### 6.1.3 Secondary Endpoints

The secondary endpoints are student academic productivity, homework, and academic grades.

### 6.1.4 Sample Size and [name]

**Number of students and statistical power.** It is anticipated that a total of 140 students will participate in the OST-S group and 140 in a treatment as usual (TAU) control group.

#### **Primary Objectives and Secondary Objectives Involving Academic Outcomes:**

As is customary, our estimates are in standard deviations (SDs; effect sizes). We examined power assuming 20 schools, inclusion of 3-4 students per grade level across two grade levels (3.5 students per school), and randomization at the school level. The design targets on average 14 students per school, or 280 total. To allow for 15% loss to follow up at the student level, we assume 120 students per arm. Each student will have data collected at 4 time points: baseline, post-treatment, 5-month follow-up, and 12-month follow-up. For analysis, we will use all available data until the time of dropout. For power calculations, we assumed conservatively a baseline measure and one follow up per student.

We accounted for the reality that longitudinal measures at the student level increase power and clustering of students within schools decreases power. We assumed three relatively modest correlations of outcome measures within student over time: 0.5, 0.6 and 0.7, which correspond to SDs of change of 1.0, 0.8, and 0.6 for a 1 SD cross sectional difference. Correlations of 0.5 lead to no increase in power from the design, and correlations of 0.6 and 0.7 correspond to approximately 10% and 20% increases in power. To account for clustering, we assumed intra-cluster correlations (ICC)=0.01, typical in school-based trials (Office of Behavioral and Social Sciences Research, NIH: <http://esourceresearch.org/tabcid/384/Default.aspx>). We also used ICC=0.038. This ICC value corresponds to variation across schools on the order of 0.4 SD of the distribution of outcome scores, or the equivalent to a range of means across schools of 1.6 SDs, a modest degree of inter-cluster variation. The design effects of these assumptions are 1.03 (small) and 1.11 (modest), to be expected with a relatively small number of students per school, and correspond to a reduction in the effective sample size of 3-11%.

[name] calculations were performed using PASS 11 (Hintze, 2011; [www.ncss.com](http://www.ncss.com)), which demonstrated 90% power to detect a change in outcomes equivalent to 0.5 or greater in cross-sectional SDs, assuming at least 12 students per school and model correlation of these scores within student over time (corr=0.7), and assuming an ICC of 0.038 (a relatively large degree of variation across schools). A change equivalent to 0.5 cross-sectional SDs in outcome scores and 12 students per school is still detectable (power>0.85) if the correlation within students over time is 0.7 and the ICC across schools is 0.038. Larger effects can be detected with greater power. These power estimates apply to both OTMP skills and academic outcomes using intervention as a binary outcome in an intent-to-treat analysis. Based on the pilot study of OST-S, we expected effect sizes for outcomes to be in the 0.6 to 0.8 range. These power calculations are likely conservative; inclusion of covariates might actually improve power.

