If these exploratory analyses reveal there is a signal indicative of a main effect of intervention condition and/or an interactive effect of intervention condition and grade level and/or an interactive effect of intervention and school subsidized lunch rate subgroup, power calculations will be performed to determine the sample size needed to conduct tests of significance for the three study goals outlined above, which are the most important study aims. We will not perform power calculations again to conduct complex mediation analyses, which require a relatively large sample size. We will base power calculations on the same assumptions outlined in the original statical analysis plan, including an expected effect size of .50 and attrition of 15%.

This is a one-time request to provide summary statistics to the project officer for the purpose of obtaining a financial supplement. **If we obtain a supplement from the funding agency, we plan to submit another amendment to the IRB to clarify aims, update power calculations, and modify the statistical analyses plan.**

---

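### Protocol 6.1.4 labels variances of change as SDs, and its 90% power cannot be traced to the inputs printed with it

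*Protocol*

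**What the plan says.** The power paragraphs of protocol 6.1.4 assume 20 schools, 120 evaluable students per arm, and a baseline plus one follow-up per student.

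- **SDs of change.** Correlations of 0.5, 0.6 and 0.7 are paired with SDs of change, "which correspond to SDs of change of 1.0, 0.8, and 0.6 for a 1 SD cross sectional difference". The next sentence adds that "correlations of 0.6 and 0.7 correspond to approximately 10% and 20% increases in power".
- **School variation.** ICCs of 0.01 and 0.038 are used. Of the second, the text says: "This ICC value corresponds to variation across schools on the order of 0.4 SD of the distribution of outcome scores". The design effects are given as 1.03 and 1.11.
- **Power.** The calculations "demonstrated 90% power to detect a change in outcomes equivalent to 0.5 or greater in cross-sectional SDs", with at least 12 students per school, correlation 0.7 and ICC 0.038. The following sentence says that 0.5 SD with 12 per school is "still detectable (power>0.85) if the correlation within students over time is 0.7 and the ICC across schools is 0.038".

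Section 6.1.4 gives no alpha and no sidedness. Section 6.1.1 specifies a mixed model in which schools may differ in slope as well as intercept. On any new power calculation, section 6.2.2 says: "We will base power calculations on the same assumptions outlined in the original statical analysis plan". The SAP states: "Statistical significance was evaluated using a threshold p value of .0083".

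**The concern.** With a cross-sectional SD of 1, the printed 0.8 and 0.6 are what 2(1 − r) gives before the square root is taken. That alone means a design input is wrong as printed.

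The two power sentences carry the same effect size, cluster size, correlation and ICC. The figures 90% and above 0.85 are compatible, but *still* signals a less favourable scenario and none is printed. One sentence has therefore probably lost or misprinted an input.

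The headline 90% also depends on something the text leaves open: whether ICC 0.038 describes the score or the change in score. The accompanying glosses (0.4 SD, design effects 1.03 and 1.11) do not fit ICC 0.038 with 12 students per school. At stake is whether a reader, or the team in a later calculation, can tell what the trial's main power statement rests on.

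**Working it through.** **Inputs from protocol 6.1.4:** d = 0.5 cross-sectional SD; 10 schools per arm; 12 students per school (120 per arm); r = 0.5, 0.6, 0.7; ICC 0.038; change from baseline to one follow-up. **Assumed:** two-sided alpha 0.05.

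**1. SD of change.** With unit cross-sectional SD, Var(change) = 2(1 − r) and SD = √[2(1 − r)].

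| r | 2(1 − r) | SD | Printed as SD | Reduction in SD from 1.0 |
|---|---|---|---|---|
| 0.5 | 1.0 | 1.000 | 1.0 | 0% |
| 0.6 | 0.8 | 0.894 | 0.8 | 10.6% |
| 0.7 | 0.6 | 0.775 | 0.6 | 22.5% |

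The protocol's own gains of about 10% and 20% fit the correct SDs. The printed SDs would imply reductions of 20% and 40%.

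**2. Trying to reproduce the 90%.** Let vb be the school variance of change and vw = 2(1 − r) − vb. Then SE = √[2(vb/10 + vw/120)] and ncp = 0.5/SE. Power comes from a noncentral t on 18 df and from the normal approximation.

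| Assumption | vb | SE | ncp | Power, t / normal |
|---|---|---|---|---|
| r = 0.7, ICC on the change score | 0.038 × 0.6 = 0.0228 | 0.119 | 4.20 | 0.978 / 0.987 |
| r = 0.7, cross-sectional ICC, school effects independent over time | 2 × 0.038 = 0.076 | 0.155 | 3.23 | 0.863 / 0.898 |
| r = 0.5, ICC on the change score | 0.038 × 1.0 = 0.038 | 0.154 | 3.25 | 0.868 / 0.902 |
| r = 0.7, school SD of change 0.4 | 0.16 | 0.198 | 2.52 | 0.665 / 0.713 |

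The first row uses only the printed inputs and gives about 98%, not 90%. The second and third rows both land near 90% and near 0.86, but each needs something the text does not say. Entering 0.6 as a literal SD, with the ICC on the change score, gives more than 0.99, so the mislabelled SD is not the source of the 90%.

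**3. Glosses on the ICC.** The school SD implied by ICC 0.038 is √0.038 = 0.195, not 0.4; a school variance of 0.4² = 0.16 within a total of 1 would be an ICC of 0.16. The design effect is 1 + (m − 1) × ICC.

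| Students per school | ICC 0.01 | ICC 0.038 |
|---|---|---|
| 4 | 1.03 | 1.11 |
| 12 | 1.11 | 1.418 |
| 14 | 1.13 | 1.494 |

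The printed pair 1.03 and 1.11 belongs to about 4 students per school.

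**4. If the printed SDs were reused.** At 12 per school, required N is proportional to vb + vw/12.

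- School variance scaling with the change variance: 0.64/0.80 = 0.80 at r = 0.6 and 0.36/0.60 = 0.60 at r = 0.7, an understatement of 20% and 40%.
- School variance fixed at 0.076: (0.076 + 0.564/12)/(0.076 + 0.724/12) = 0.902 and (0.076 + 0.284/12)/(0.076 + 0.524/12) = 0.833, an understatement of about 10% and 17%.

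**5. At the SAP threshold of 0.0083** (0.5 SD, r = 0.7; t / normal): 0.874 / 0.941 with the ICC on the change score, and 0.610 / 0.723 with independent school effects. These are approximations. They do not model the SAP's splines, weights, repeated follow-ups or random slopes.

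**The case against.** The best defence is that nothing of consequence follows. The 10% and 20% gains show that the authors had the right SDs in mind, so the 0.8 and 0.6 are a misprint. The two power figures do not contradict each other, and a cross-sectional ICC with independent school effects returns both (0.898 and 0.863). The protocol describes the ICC on the scale of outcome scores, which leans that way. Section 6.2.2 names only the effect size of 0.50 and attrition of 15% among the assumptions to be reused, and foresees a further amendment with updated power if a supplement is obtained. The SAP is written in the past tense, so power restated at its threshold cannot alter the sample size. The protocol also expected effects of 0.6 to 0.8 SD, above the 0.5 used here.

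Most of this stands, and it limits the point. A reader might infer that the variance slip inflated the 90%; the arithmetic shows it did not. A reader might infer that N will be understated by 40%; that needs both reuse of the printed SDs, which 6.2.2 does not state, and school variance that shrinks with the change variance. A reader might also treat the missing power at 0.0083 as an error; it is a gap in reporting.

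What the defence does not remove is that two printed SDs are wrong and that one scenario appears twice. Independence of school effects over time is a reconstruction, and a true correlation of 0.5 explains the figures equally well. The design effects and the 0.4 SD conflict with the stated ICC and cluster size.

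**Conclusion.** Wrong as written, and worth correcting as a matter of reporting. The SD labels, the duplicated inputs, the design effects and the 0.4 SD gloss are checkable from the text and certain. That the 90% cannot be reproduced is held with moderate confidence, because the software run is not available and alpha is assumed. Section 6.1.5 speaks of conventional significance for mediation and 6.2.2 uses 95% intervals, which makes two-sided 0.05 a reasonable assumption but not a stated one.

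The documents do not support a claim that the trial is underpowered. On the printed inputs with the ICC on the change score, power at 0.05 exceeds the stated 90%. It falls clearly below, to about 0.67 to 0.71, only if the school SD of change really is 0.4.

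**What to change.** In protocol 6.1.4:

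1. Correct the SDs of change to 1.0, 0.89 and 0.77.
2. Correct or delete the duplicated scenario so that each power figure carries the inputs actually used.
3. Reconcile the design effects 1.03 and 1.11 with 12 students per school (1.418 at ICC 0.038), and the 0.4 SD with ICC 0.038 (school SD about 0.195).
4. State alpha, sidedness, and whether the ICC applies to the score or to the change. If it applies to the score, give the school-level correlation over time.
5. Rerun and restate the power on those inputs.

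Power at 0.0083 may be reported alongside, with the analysis model and degrees of freedom named, as a disclosure and not as the correction of an error.

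The cost is some protocol wording and one rerun of the power software. Sample size, design and analysis are untouched.
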